6.2 The Clinical Practice Research Database (CPRD) paediatric FH cohort

CPRD RDG Protocol ID: 22-002278

The CPRD will be used as a secondary source of data to assess LLT treatment and potential sideeffects in children with FH, as well as medication adherence. This provides detailed longitudinal electronic health records from primary care with linkages to hospital admissions (but no access to specialist lipid clinic records). The general population in CPRD is highly representative of the sociodemographic distribution across the UK.¹¹ Our current unpublished research using CYP in the general population shows good national representation across socioeconomic and ethnic groups. Our June 2021 feasibility assessment of all CYP with diagnostic codes for FH in the CPRD GOLD database (which contains ~27% of the CPRD general population) showed they had a mean diagnosis age of 11 years, mean active follow-up 9 years, 64% were prescribed statins before age 18, and the mean number of LDL-C measures was 3, with almost half (42%) having prospective clinical records into adulthood. Using the whole of CPRD (GOLD and Aurum), we estimate at least 2,000 CYP with coded FH and another 1,600 with the clinical phenotype (based on our assessment of statin prescribing and hypercholesterolaemia coding). CPRD has reasonably complete information for these patients' gender, socioeconomic group, ethnicity, body mass index (BMI), however, it lacks the level of information on potential confounders that are available from the PFHR.

6.3 The Avon Longitudinal Study of Parents and Children (ALSPAC) cohort for deriving average cholesterol across childhood in the general (non-FH) population

ALSPAC Reference (B Number): B3815

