LDL-C changes in those exposed to LLT will be compared with changes in those never exposed or unexposed up to a certain age, measured as the difference between the earliest and later follow-ups. We will use inverse probability of treatment weighting techniques^{28,29} to balance exposed and unexposed groups according to both baseline and time-varying measured confounders: family history of CVD and/or FH in family, gender, genetic testing, body mass index (BMI), ethnicity, other health conditions, reasons for not being on LLT or non-adherence, process factors such as attendance frequency, and socioeconomic deprivation (using post-code linkage to index of multiple deprivation).

We will primarily estimate intention-to-treat effects, i.e. the effect of prescribing LLT to children with FH on LDL-C levels.³⁰ We will then estimate per-protocol effects, which corresponds to the effect of continuously taking LLT during the following period. Potential treatment non-adherence and loss to follow-up will be accounted for via censoring weights.³⁰ Missing data in both the LDL-C outcomes and confounders will be addressed using multiple imputation.

We will conduct sensitivity analyses to assess the extent to which the effects of age and LDL-C at initiation are robust to potential unmeasured confounding. We will adopt the E-value approach,³¹ which essentially explores how strong (association with both LLT initiation and LDL-C outcomes) the unmeasured confounders need to be to change the study conclusions. These analyses will be informed by discussions with clinical specialists and PPIE groups, and the HCP questionnaire.

This will be a descriptive analysis with the ultimate aim to derive effectiveness estimates that will feed into the cost-effectiveness model, where uncertainty will be fully propagated.³² However, initial assessment, based on pre- and post-puberty in current PFHR data shows children initiating LLT before age 12 years achieved a mean reduction in LDL-C of 2.199 after initial mean levels of 6.115 (pooled SD=2.51) and those initiating LLT at 12 or older achieved a mean reduction in LDL-C of 1.748 after initial mean levels of 5.570 (pooled SD=1.53). Demonstrating this difference at 90% power and 0.05 significance level with a 60-40 allocation ratio (as in the current Register) would require 560 children initiating LLT before age 12 and 376 initiating LLT at 12 or older, which is within our planned recruitment target.

Secondary analyses:

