- In the PFHR, we will also assess total cholesterol, HDL-C, triglycerides, and non-HDL changes
- Using the CPRD (primary care database), we will repeat LDL-C analyses in the larger sample of FH patients who may also represent a more diverse population.

Analysis (b): **Cumulative LDL-C** (cholesterol burden) will be calculated as area under the age trajectory of LDL-C between age 8 and 18 years using a linear mixed-effects model, following methods described by our collaborator [name].^{18,33} LDL-C trajectories of CYP with current exposure to LLT will be compared with those never exposed or unexposed up to a certain age. We will also calculate **TWA LDL-C** (cumulative LDL-C divided by time) as a measure of average LDL-C burden. We will use the same approach as in analysis (a) to model associations with age and LDL-C at LLT initiation and to address potential confounding. Building on the current PFHR and 3.5-year prospective follow-up, we expect to have at least 4 LDL-C measures available on most CYP. Since we will have representation

across all ages, we will also create models where we impute un-observed LDL-C using previously described methods.³⁴

Analysis (c): Achievement of treatment LDL-C targets before and after puberty, and at age 18 will be estimated using logistic regression, assessing confounding and other biases as in analysis (a). We will evaluate by age and LDL-C threshold at LLT initiation, the achievement of (i) recommended targets of 30-50% reduction or <3.5mmol/l^{5,15} and (ii) general (non-FH) population expected LDL-C levels obtained from analyses of the ALSPAC cohort data.

Using the ALSPAC cohort, we will derive population-expected LDL-C levels across childhood and adolescence using longitudinal measures on approximately 7,000 non-FH children to estimate LDL-C trajectories with a linear mixed-effects model of LDL-C against age. To describe how LDL-C trajectories vary by gender, ethnicity, and key growth and health measures such as weight-for-age, weight-for-height z-scores, fat-free mass and blood pressure, we will fit models with and without interaction terms between age splines and these factors.³³ This variation will be used in our models of target LDL-C (e.g., trajectory variation between boys and girls). Our protocol for this was approved by ALSPAC in June 2021.

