We selected data sources for Module (b) given our recently completed study on FH.²⁵ This represents the most up to date and UK-relevant evidence on long-term outcomes in adult patients with FH and aligns, as far as possible, with cost-effectiveness analyses that informed the NICE FH guideline. The effect size between LDL-C over time and CVD risk later in life is a key driver of long-term benefits from treatment and requires follow-up beyond the reach of the PFHR follow-up that is possible in this 5-year study. A pragmatic review will be conducted to identify high-quality evidence, such as large individual patient data meta-analyses, that quantifies the impact of high LDL-C from childhood/early adulthood on later CVD morbidity and mortality.

Inputs for Module (b) on outcomes in adulthood:

Parameter	Source
Relationship between LDL-C over time and CVD risk later in life	Pragmatic review of studies evaluating the impact of high LDL-C from childhood/early adulthood on long-term CVD risk
Risk of CVD in adulthood	Risk equations from our previous work on a UK cohort of patients with FH (N=2,135, median follow-up 4.8 years)
Risk of non-cardiovascular death	General population statistics
Mortality risk following a first non- fatal cardiovascular event	Risk equations from our previous work, based on the risk observed in patients with FH and UK general-population study
Costs of LLT and of routine FH management	Current clinical guidelines for adults and expert advice
Costs of care post-cardiovascular events	Costs from an analysis of UK routine data of patients with coronary disease
Health-related quality of life prior to cardiovascular events	UK general population norms
Health-related quality of life post cardiovascular events	UK general population norms, adjusted for the impact of cardiovascular events based on previous cost-effectiveness analyses to inform NICE guidelines

Uncertainty: The model will reflect the parameter uncertainty in the module inputs via probabilistic sensitivity analysis. We will conduct extensive scenario analyses to the key assumptions. Examples include using estimates of effect of LLT on LDL-C from CPRD analysis rather than those obtained from PFHR in Objective 1, calculating NHS management costs based on clinical guideline recommendations rather than those estimated in Objective 5, using alternative relationships between LDL-C and long-term CVD risk identified by the pragmatic review.

Output

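### The CPRD cohort counts about 1,600 of some 3,600 children as FH partly from statin prescribing, and nothing keeps them out of the treated-versus-untreated LDL-C comparison

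*Protocol*

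**What the plan says.** Protocol section 6.2, under the heading of the CPRD paediatric FH cohort, builds the estimated cohort from two groups. For the first, "we estimate at least 2,000 CYP with coded FH". The second is "another 1,600 with the clinical phenotype (based on our assessment of statin prescribing and hypercholesterolaemia coding". In the feasibility work in CPRD GOLD, which holds about 27% of the CPRD population, "64% were prescribed statins before age 18" among children with FH codes. The same section says that "The CPRD will be used as a secondary source of data to assess LLT treatment" and concedes that "it lacks the level of information on potential confounders that are available from the PFHR".

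Section 7.1, analysis (a), defines the comparison: "LDL-C changes in those exposed to LLT will be compared with changes in those never exposed or unexposed up to a certain age". Its primary estimand is the effect of prescribing LLT. Under the secondary analyses, for CPRD, "we will repeat LDL-C analyses in the larger sample of FH patients".

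Section 7.6 lists both PFHR and CPRD results as sources for the effect of LLT on LDL-C. Its uncertainty paragraph gives as an example scenario "using estimates of effect of LLT on LDL-C from CPRD analysis rather than those obtained from PFHR".

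**The concern.** The phenotype group is found in part through the exposure under study. Take a child with no FH code who enters because a statin was prescribed. That child is treated by construction. A child with similar lipids, no FH code and no statin may never enter. Two things follow for the prescription-identified children:

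- They supply no never-treated comparators.
- Their time before the statin can count as unexposed up to a certain age, but they are in the data only because treatment came later. Similar children who never went on to a statin are missing from that unexposed time.

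The CPRD result is meant to corroborate the PFHR result and may replace it in a model scenario. If treated and untreated children reach the cohort by different routes, agreement or disagreement between the two sources could reflect how children were found and not what treatment does.

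**Working it through.** **The plan's own figures.** The 2,000 and 1,600 are feasibility estimates given without derivation, so they can be added but not reproduced. 2,000 + 1,600 = 3,600, and 1,600 / 3,600 = 44% of the estimated cohort. The sample-size calculation in section 7.1 concerns early versus late initiators in the PFHR and has no bearing here.

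**Inputs**
- Coded children: 2,000 (section 6.2, stated as a minimum).
- Phenotype children: 1,600 (section 6.2).
- Statin share among coded children: 64% before age 18 (section 6.2). This is a GOLD figure; that it holds across all of CPRD is an assumption.
- f, the share of the 1,600 who needed a prescription to be counted: not stated. Section 6.2 names prescribing and hypercholesterolaemia coding without saying whether both or either is required, so a range is shown.
- Phenotype children not admitted by prescription are taken as untreated (an assumption).

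**Coded group alone.** Treated: 0.64 × 2,000 = 1,280. Untreated: 2,000 − 1,280 = 720.

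**Both groups.** Treated = 1,280 + 1,600f. Untreated = 3,600 − treated. Prescription-identified share of the treated = 1,600f / (1,280 + 1,600f).

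| f | Prescription-identified | Treated | Untreated | Share of treated |
|---|---|---|---|---|
| 50% | 800 | 2,080 | 1,520 | 800 / 2,080 = 38% |
| 75% | 1,200 | 2,480 | 1,120 | 1,200 / 2,480 = 48% |
| 100% | 1,600 | 2,880 | 720 | 1,600 / 2,880 = 56% |

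At f = 100% the treated are 2,880 / 3,600 = 80% of the cohort, and all 720 never-treated children come from the coded group.

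The assumption about the remaining phenotype children matters at lower f. If 64% of them were treated as well, then at f = 50% the treated number 2,080 + 0.64 × 800 = 2,592, and the share is 800 / 2,592 = 31%.

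**Do the planned methods deal with this?** Section 7.1 names four safeguards:
- Inverse probability of treatment weighting balances measured confounders. Among prescription-identified children the probability of ever being treated is 1, so no never-treated child of that kind exists to be weighted up (positivity fails).
- Censoring weights address non-adherence and loss to follow-up.
- Multiple imputation addresses missing outcomes and confounders.
- The E-value addresses unmeasured confounding.

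None of them addresses entry to the cohort that depends on the exposure.

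**The case against.** The strongest reply is that a feasibility count is not an entry rule. Section 6.2 gives no CPRD eligibility criteria and cites a separate CPRD protocol that is not at hand, where phenotype definitions and analysis sets may be fixed. The larger sample in section 7.1 need not mean 3,600: the 2,000 coded children alone exceed the PFHR target of 1,374 in section 6.1.1. This stands in part. A reader might infer that all 1,600 certainly enter the comparison, or that every one of them is treated. The text says neither. What remains is that the 1,600 are presented as part of the cohort, an exposure-based route is named, and no boundary is set on its use.

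Second, much of Objective 1 concerns reductions from pre-treatment levels by age and LDL-C at initiation. Those comparisons are among initiators and need no never-treated children. This stands, and the fix respects it.

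Third, a reader might infer from the head counts that the CPRD estimate is biased by a known amount or in a known direction, or might call the pre-statin time immortal. The documents support neither. The counts show how much of the treated group could be affected, not how far the LDL-C effect would move. Because the outcome is change in a repeated measure and not an event, selection on later treatment is the more accurate description.

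Fourth, CPRD is a secondary source, and section 7.6 makes the use of several sources depend on their quality and relevance. This limits the consequence but does not remove the problem from the CPRD comparison.

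**Conclusion.** The point holds as a gap that should be closed. As written, the protocol allows children found through statin prescribing into a comparison whose exposure is prescribing, and its planned methods do not correct for that. For f between 50% and 100%, prescription-identified children would be 38% to 56% of treated CPRD children. That range rests on the GOLD 64% applying to all coded cases and on the other phenotype children being untreated. The problem arises for any f above zero.

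It would be wrong to conclude that the study's main result is compromised. The primary LDL-C estimate comes from the PFHR and is not affected. What is exposed is the CPRD repeat and whatever use section 7.6 makes of it.

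**What to change.** State in section 6.2 or 7.1 that CPRD treated-versus-untreated comparisons (LDL-C, and any on growth or safety) use children with an FH diagnostic code, or a phenotype defined only from lipid values and codes without reference to prescribing. Keep LDL-C values recorded before the FH code as baselines. Starting follow-up at the code date could discard pre-treatment values, and section 6.2 reports a mean of only 3 LDL-C measures per child.

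Use the statin-identified group for analyses among initiators: LDL-C reduction by age and LDL-C at initiation, prescription possession ratio, and discontinuation. Include it in the treated-versus-untreated comparison only as a labelled sensitivity analysis. State whether the phenotype requires both criteria or either one.

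The cost is a few sentences and a smaller CPRD comparison, about 2,000 children in place of 3,600 if only coded children are used. If the separate CPRD protocol already sets this boundary, a cross-reference is enough.

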6.4 Questionnaire and interview study with healthcare professionals working in paediatric FH

UoN FMHS REC reference: FMHS 253-0423

6.4.1 Protocol summary

Currently, treatment of paediatric FH remains secondary and tertiary care led. This study will collect questionnaire and interview data from HCPs currently involved in the clinical diagnosis and followup management of CYP with FH, in centres throughout the UK. It will provide data on and insight into current treatment practices in contemporary FH management in CYP, from lifestyle management to LLT, and from diagnosis to transfer to adult services. It will provide information on variation in clinical practice (routine practice/criteria on decisions to initiate LLT, treatment targets, adherence monitoring, starting dose, changing dose, and type/frequency of specialist healthcare provision) and the factors that influence this. Information will be used to describe the current clinical landscape and as variables in the PFHR analyses of clinical and cost-effectiveness, to account for clinical variation across sites in factors such as treatment targets.

There are no available estimates of the number of HCPs working in paediatric FH in the UK. Based on the existing PFHR clinical network and informal professional networks organised by the UK cholesterol charity HEART UK, we estimate 50-100 HCPs will complete questionnaires and we will interview 30 HCPs.

6.4.2 Eligibility criteria

Healthcare professionals involved in the clinical care of CYP with FH within the UK NHS (i.e., paediatric FH care) are eligible to participate. Participants may be from any clinical specialty/job role and may also work in adult care, but some of their role must be with paediatric FH patients.

6.4.3 Inclusion criteria

- Healthcare professionals involved in the clinical care of CYP with FH within the UK NHS (i.e., some involvement in paediatric FH care)
- Participants should be currently working in their clinical role or have worked in this role within the past 10 years

6.4.4 Exclusion criteria

• Not meeting inclusion criteria

6.4.1 Recruitment and consent procedure

Due to the diversity and complexity of HCPs working in paediatric FH, including dieticians, pharmacists, specialist nurses and physicians from a broad range of specialities, no formalised method of contact via NHS communication channels exists. Recruitment will utilise professional networks and contacts. The study will be advertised in the newsletter of HEART UK and through the linked Lipid Intelligence Network, which brings together different types of professionals with an interest in blood lipids. It will also be advertised to the Lipid Interest Group (a shared learning group open to nurse specialists and allied professionals) and at the HEART UK conference in July 2023. HCPs contributing the to PFHR and contacts of those participating in the PFHR network will be approached.

Questionnaire recruitment: HCPs will be invited (via above methods) to fill in an online questionnaire on their insight/ views on factors that influence diagnosis, and initiating and maintaining LLT in CYP. Questionnaire participants can express an interest in being contacted for further research and may be invited for follow up interviews to gain further narrative information on current practice and its determinants.

Semi-structured interview recruitment: Health professionals who provide the paediatric FH service will be purposely sampled to participate in semi-structured interviews. It is envisaged this group will comprise paediatric cardiologists, lipidologists, metabolic medicine specialists, endocrinologists, nutritionists, and specialist genetic or FH nurses covering diverse healthcare settings. Some will have completed the online questionnaire and indicated an interest in being interviewed, but others may be recruited directly for interviews. Therefore, our sampling approach will combine both convenience (self-selecting individuals opting to take part or be contacted, and subsequent completion of eligibility) and purposeful approaches. We will purposefully invite individuals representing specific criteria, to ensure we capture a range of perceptions and experiences:

- Large and small clinical sites
- Services led by different specialities (e.g., paediatrics, metabolic medicine, cardiology)

- Services using and not using specific clinical protocols
- Different types and grades of HCP
- Geographic location of site

Informed consent for questionnaire and/or interview data collection: Potential participants will require online access to complete the consent form or it can be completed via posted paper form or telephone. Consent forms will be signed and dated by the individual before any relevant data are collected. Electronic formats will be via the REDCap secure web application.

Should there be any subsequent amendment to the final protocol that might affect a participant's participation in the study, continuing consent will be obtained using amended consent forms which will be signed by the participant.

6.4.1 Participant commitment and data collection

Questionnaire data collection: Following provision of consent, participant individuals will complete one self-administered questionnaire, comprising a mix of closed and open-ended questions, using the REDCap web application, paper questionnaire or questionnaire administered via telephone with the researcher using the REDCap web application.

Semi-structured interviews: Following provision of consent, participants will undergo an interview of up to 1 hour conducted via telephone or online using Microsoft Teams (or in-person if telephone or online methods are not practical). All interviews will be recorded using a handheld digital audio recorder. For interviews conducted online using Microsoft Teams, the transcription utility will be used to transcribe the interview without the use of audio-visual recording; the audio recording will be retained as a backup for listening to any sections of interview where the text transcription file is unclear.

6.4.1 Participant withdrawal

Participants will be free to withdraw (i.e., to stop completing the questionnaire or stop the interview) at any time without giving a reason. In addition, the research team may discontinue a participant's participation from the study at any time they consider it necessary for any reason including:

- Withdrawal of consent
- Incomplete/unusable data

When a participant withdraws from further participation, any information already obtained will be retained and may still be used in the final study analyses (this will be made clear in information sheets and consent forms).

7 Analysis

7.1 Objective 1: Estimate absolute and relative reductions in LDL-C, and in cumulative LDL-C, achieved in current practice with LLT, and whether these vary by age and LDL-C at initiation of LLT

Methods: We will evaluate the effectiveness of initiating LLT at different ages and LDL-C thresholds (at baseline) on LDL-C levels measured at **routine follow-up visits recorded in the PFHR** (and **secondarily in the CPRD FH population**). We will:

(a) estimate absolute and % reductions in LDL-C from pre-treatment levels, which will then be incorporated into the economic model,

(b) estimate cumulative LDL-C and time-weighted average (TWA) LDL-C, the latter providing an estimate of average LDL-C burden over childhood and adolescence,

(c) evaluate achievement of treatment targets, using expert-consensus recommendations for FH^{5,15} and average age-specific LDL-C levels in the general (non-FH) population (derived from CYP in the ALSPAC cohort),

(d) address potential evidence gaps by updating our current systematic review of statin trials in children with FH² to include all LLT and a new pragmatic review of high-quality observational evidence.

Analysis (a): **Absolute (mmol/L) and % reductions in LDL-C** from pre-treatment levels associated with age and LDL-C at LLT initiation will be estimated using a linear mixed-effects model. A multi-level structure will be used to account for children being grouped at clinical sites, with site as a random effect.

LDL-C changes in those exposed to LLT will be compared with changes in those never exposed or unexposed up to a certain age, measured as the difference between the earliest and later follow-ups. We will use inverse probability of treatment weighting techniques^{28,29} to balance exposed and unexposed groups according to both baseline and time-varying measured confounders: family history of CVD and/or FH in family, gender, genetic testing, body mass index (BMI), ethnicity, other health conditions, reasons for not being on LLT or non-adherence, process factors such as attendance frequency, and socioeconomic deprivation (using post-code linkage to index of multiple deprivation).

We will primarily estimate intention-to-treat effects, i.e. the effect of prescribing LLT to children with FH on LDL-C levels.³⁰ We will then estimate per-protocol effects, which corresponds to the effect of continuously taking LLT during the following period. Potential treatment non-adherence and loss to follow-up will be accounted for via censoring weights.³⁰ Missing data in both the LDL-C outcomes and confounders will be addressed using multiple imputation.

We will conduct sensitivity analyses to assess the extent to which the effects of age and LDL-C at initiation are robust to potential unmeasured confounding. We will adopt the E-value approach,³¹ which essentially explores how strong (association with both LLT initiation and LDL-C outcomes) the unmeasured confounders need to be to change the study conclusions. These analyses will be informed by discussions with clinical specialists and PPIE groups, and the HCP questionnaire.

This will be a descriptive analysis with the ultimate aim to derive effectiveness estimates that will feed into the cost-effectiveness model, where uncertainty will be fully propagated.³² However, initial assessment, based on pre- and post-puberty in current PFHR data shows children initiating LLT before age 12 years achieved a mean reduction in LDL-C of 2.199 after initial mean levels of 6.115 (pooled SD=2.51) and those initiating LLT at 12 or older achieved a mean reduction in LDL-C of 1.748 after initial mean levels of 5.570 (pooled SD=1.53). Demonstrating this difference at 90% power and 0.05 significance level with a 60-40 allocation ratio (as in the current Register) would require 560 children initiating LLT before age 12 and 376 initiating LLT at 12 or older, which is within our planned recruitment target.

Secondary analyses:

- In the PFHR, we will also assess total cholesterol, HDL-C, triglycerides, and non-HDL changes
- Using the CPRD (primary care database), we will repeat LDL-C analyses in the larger sample of FH patients who may also represent a more diverse population.

Analysis (b): **Cumulative LDL-C** (cholesterol burden) will be calculated as area under the age trajectory of LDL-C between age 8 and 18 years using a linear mixed-effects model, following methods described by our collaborator [name].^{18,33} LDL-C trajectories of CYP with current exposure to LLT will be compared with those never exposed or unexposed up to a certain age. We will also calculate **TWA LDL-C** (cumulative LDL-C divided by time) as a measure of average LDL-C burden. We will use the same approach as in analysis (a) to model associations with age and LDL-C at LLT initiation and to address potential confounding. Building on the current PFHR and 3.5-year prospective follow-up, we expect to have at least 4 LDL-C measures available on most CYP. Since we will have representation

across all ages, we will also create models where we impute un-observed LDL-C using previously described methods.³⁴

Analysis (c): Achievement of treatment LDL-C targets before and after puberty, and at age 18 will be estimated using logistic regression, assessing confounding and other biases as in analysis (a). We will evaluate by age and LDL-C threshold at LLT initiation, the achievement of (i) recommended targets of 30-50% reduction or <3.5mmol/l^{5,15} and (ii) general (non-FH) population expected LDL-C levels obtained from analyses of the ALSPAC cohort data.

Using the ALSPAC cohort, we will derive population-expected LDL-C levels across childhood and adolescence using longitudinal measures on approximately 7,000 non-FH children to estimate LDL-C trajectories with a linear mixed-effects model of LDL-C against age. To describe how LDL-C trajectories vary by gender, ethnicity, and key growth and health measures such as weight-for-age, weight-for-height z-scores, fat-free mass and blood pressure, we will fit models with and without interaction terms between age splines and these factors.³³ This variation will be used in our models of target LDL-C (e.g., trajectory variation between boys and girls). Our protocol for this was approved by ALSPAC in June 2021.

Analysis (d): A **systematic review and a pragmatic review** will address potential evidence gaps for the economic model. Effect estimates of LLT effectiveness (and safety for objective 2) will be pooled using meta-analysis where appropriate. Our 2019 Cochrane review of statin trials in children with FH¹⁴ identified only short-term LDL-C reduction and safety (median follow-up in trials 5.5 months). We will update this systematic review with any new randomised control trial evidence and expand it to include ezetimibe given its increasing use.⁴⁸ Due to a lack of long-term trial evidence, a **pragmatic review of high-quality observational studies with data on longer-term effectiveness and safety** will be conducted. It will prioritise high-quality registry and cohort evidence (defined by risk of bias criteria e.g., ROBINS-I), followed by long-term extension studies as relevant to inform the economic model. Eligible outcomes will include changes in LDL-C, growth and maturation, CVD and safety outcomes.

Outputs

- Parameters for economic model (Objective 6): absolute and % LDL-C reductions according to age and LDL-C thresholds at LLT initiation
- Identify how cumulative LDL-C up to age 18 is affected by age and LDL-C thresholds at LLT initiation
- Identify how achievement of LDL-C treatment targets is affected by age and LDL-C thresholds at LLT initiation

7.2 Objective 2: Estimate the incidence of side-effects and adverse events associated with LLT

Methods: The following data sources will be used to assess LLT safety (side-effects, adverse events, growth and development effects):

1. **PFHR** data captures adverse events through blood tests (raised level of creatine kinase, aspartate and alanine transaminase), documenting clinical features (e.g., rhabdomyolysis), and newly added data items on patient-reported side-effects such as muscle weakness or pain symptoms. Weight, height and age at first menstruation will be assessed as measures of growth and development.

2. **CPRD** data on hospital admissions or general practice attendance will be used to assess sideeffects and adverse events. We will use post-marketing side-effects reported for each LLT type (e.g., headache, dizziness, unusual weakness, sleep problems). CPRD will provide a large sample to assess adverse events (e.g., rhabdomyolysis) as these will be extremely rare according to current evidence in adults.³⁵ Safety across childhood and into early adulthood will be assessed (with 42% of children with FH having CPRD records into adulthood).

3. Potential gaps will be addressed by the **systematic and pragmatic reviews**, as described in objective 1, that will include short and longer-term rare or serious side-effects of LLT including ezetimibe.

Analysis: Among children on LLT, liver enzyme (transaminases) measures >2.5 times the upper limit of normal before and after puberty will be described according to LLT type (of statin and more rarely used medications such as ezetimibe) and dose. Logistic regression models will be used to adjust for clinical and sociodemographic factors.

Age at first menstruation, weight-for-age and weight-for-height z-scores (BMI in adolescents) according to LLT exposure (type, dose, age at initiation) will be modelled using generalized estimating equations/growth models adjusting for clinical and sociodemographic factors.

Incidence rates of side-effects and adverse events will be described according to LLT exposure (type, dose, age at initiation) and Poisson regression will be used to adjust for clinical and sociodemographic factors.

Outputs

- Incidence of side-effects and adverse events
- Effects of LLT on growth and development
- Parameters for economic model (Objective 6): LLT adverse event rates

7.3 Objective 3: Estimate LLT adherence at different ages and characterise reasons for variations in adherence

Methods: We will measure adherence and characteristics related to variation in adherence using:

(a) Adherence captured at **routine follow-up visits recorded in the PFHR.** Based on discussions with our clinical specialist collaborators and Nottingham CYPAG and our PPIE group, these items will indicate recent adherence and reasons for sub-optimal adherence.³⁶

(b) **Patient questionnaires at baseline, 8, 16, 24 months** to obtain changes in adherence over time incorporating the Medication Adherence Report Scale.²⁷ The study CYPAG and PCAG will support interpretation of the questionnaire results.

(c) Repeat prescription information from CPRD records of CYP with FH as an adherence proxy

Analysis (a) and (b): Following descriptive analysis, generalized estimating equations for repeated measures analysis will be used to examine associations of high adherence (versus low/moderate) with age, gender, ethnicity, deprivation, frequency of LDL-C testing and clinic visits, age and LDL-C level at LLT initiation, reasons for sub-optimal adherence, reported side-effects and family history of CVD.

Analysis (c): Using electronic LLT prescriptions, we will calculate the number of days individuals are prescribed compared with periods of active general practice registration. Missing information on prescription duration or dose will be imputed using prior published methods.^{21,23} We will calculate a prescription possession ratio (PPR) over specified periods of time (e.g., annual PPR (%)= total days prescribed LLT/days of GP registration over 1 year).^{21,23} We will estimate how the PPR is associated with current age and age at first LLT prescription, gender, deprivation and ethnicity. We will model factors associated with time to discontinuation using Cox regression, similar to an approach used in a US study on LLT prescribing in young people²² and estimate the proportion of children maintaining LLT prescriptions into adulthood.

Outputs

- Patterns of medication adherence and characterisation of low/high adherence by age
- Factors associated with non-adherence triangulated between the Register, patientquestionnaires and CPRD

• Parameter for economic model (Objective 6): proportion of young people with FH who remain on treatment at age 18

7.4 Objective 4: Understand the views of children and young people, their families and healthcare professionals, on information needs for starting LLT at different ages, and how these influence treatment acceptability, monitoring, and adherence

Methods: We will use data from the qualitative semi-structured interviews with CYP, their parents/families and HCPs involved in the treatment and monitoring of young people with FH.

Analysis: Interview audio data will be transcribed verbatim. Data will be analysed using the framework approach, which is a hierarchical, matrix-based method developed for applied research.³⁷ The framework will enable us to map thematic differences/similarities within and between groups, such as by age at LLT initiation or adherence. Data will be coded both according to a priori themes and inductively. Initial readings will facilitate familiarisation and will lead to the generation of codes. Further analysis will result in more substantive themes and sub-themes (the analytical framework). Data will then be indexed according to the analytical framework. A sub-sample of data will be double coded to ensure validity of interpretations. We will also incorporate respondent validation whereby young people and parents will be invited to check initial accuracy of transcripts, add to them after a period of reflection, and review whether mapped themes are a reasonable reflection of their data. Finally, themes will be discussed and agreed between the research team, allowing clarification of the final framework that will then be applied across all transcripts.

The collected qualitative data will complement and clarify the quantitative findings by helping to identify common themes, and possible explanations.

Outputs

- Identification of barriers and facilitators to treatment adherence considering the role of age at initiation, access to care/monitoring and triangulation with questionnaire findings (e.g., accounting for differences according to demographics)
- Identification and description of the information needs for starting LLT at different ages and how these maybe met
- Triangulation of findings from questionnaire and interviews with children, young people, parents and healthcare professionals to propose recommendations for how to best implement health service provision for treatment initiation and monitoring.

7.5 Objective 5: Estimate the impact of initiating LLT at different ages on the costs of managing FH over the short-term in children and young people

Method: To inform the cost-effectiveness model (Objective 6), we will estimate NHS costs of managing CYP with FH and the effect of starting LLT on costs using data on healthcare use (e.g., outpatient appointments, GP visits) **collected from PFHR patient questionnaires and HCP questionnaires**, as the preferred option for capturing most FH secondary care and a common method used in trials.²⁴

